7.4.2 Sensitivity analysis

The sensitivity analysis to the primary analysis, will be performed on the Treated Set (TS) using the Full follow-up period.

An additional sensitivity analysis of Time to Treatment Discontinuation or Relapse will be performed using the same model as the primary analysis and using the same subject sets, i.e. FAS using the ITT follow-up period. This endpoint is a composite endpoint as defined above in the primary analysis, however it includes discontinuation as an outcome event.

7.5 SECONDARY ENDPOINT(S)

7.5.1 Key secondary endpoint(s)

The hypothesis testing strategy for key secondary endpoints is described in **Section 7.2 of the revised CTP:**

The remaining alpha after the testing of the primary endpoint (Steps 1 and 2) will be used to test the key secondary endpoint of change from baseline in PANSS positive symptoms. The hypotheses to be tested are:

 $H_{0(3)}$: Mean change from baseline of PANSS positive symptom score after 28 weeks of treatment with BI 409306 \geq Mean change from baseline of PANSS positive symptom score after 28 weeks of treatment with placebo

vs

 $H_{a(3)}$: Mean change from baseline of PANSS positive symptom score after 28 weeks of treatment with BI 409306 < Mean change from baseline of PANSS positive symptom score after 28 weeks of treatment with placebo

The first of the key secondary hypothesis to be tested will be based on the pooled active treatment arms (i.e. BI 409306 50 mg q.d. and BI 409306 25 mg q.d.), over 28 weeks (excluding the withdrawal/taper period).

Similar to the primary endpoint, if the first hypothesis test (on the pooled doses) is determined to be statistically significant, the individual doses will be tested for superiority using Hochberg's step-up test as described above.

The key secondary analysis will be performed on the FAS, and is described in **Section 7.3.2** of the revised CTP:

The key secondary analysis is a restricted maximum likelihood (REML) based approach using a mixed model with repeated measurements (MMRM) comparing the change from baseline of PANSS positive symptoms score after 28 weeks of treatment (Section 7.2). The analysis will include the fixed, categorical effects of treatment at each visit, and the fixed continuous effects of baseline at each visit. Visit will be treated as the repeated measure with an unstructured covariance structure used to model the within-patient measurements. The statistical model will be as follows:

$$y_{ijkm} = \beta_j S_i + \tau_{jk} + \phi_m + e_{ij}$$

 $e_{ij} \sim N_Z(\mathbf{0}, \boldsymbol{\Sigma}).$

 y_{ijkm} = response variable for subject i in country m at visit j receiving treatment k

 S_i = the baseline measurement of subject i, i=1,2,...

 β_i = coefficient of baseline effect at visit j

 τ_{jk} = the effect of treatment k at visit j, j=1,...,Z and k=1,...,Y

```
\phi_m = the effect of country m, m=1,...,X

e_{ij} = the random error associated with the j^{th} visit of the i^{th} subject. Errors are independent between subjects.

\Sigma = an unstructured covariance matrix.
```

The Kenward-Roger approximation will be used to estimate denominator degrees of freedom and adjust standard errors. Significance tests will be based on least-squares means using a two-sided $\alpha = 0.05$ or the remaining alpha (two-sided ((1- α)% confidence intervals). The treatment comparison will be the contrast between treatments at the endpoint visit.

The key secondary analysis will be performed on the FAS. Patients will be analysed according to the stratum to which they belong (regardless of any mis-assignment to treatment based on identification of the wrong stratum), as such an error occurs before randomisation and is therefore consistent with regulatory guidance.

```
[...]
```

To assess the homogeneity of the treatment effect on the key secondary endpoint across the levels of the country stratification, the same MMRM model will be fitted but replacing the treatment-by-visit term by a treatment-by-country-by-visit term. A descriptive p-value of treatment effect homogeneity at 28 weeks will be calculated. No overall treatment effect will be estimated from this model as it is not interpretable.

The following SAS code will be used:

In case the model described in the revised CTP fails to converge, the following methods will be attempted (in order) to overcome it:

- 1. Add the 'singular=1e-10' option in the model statement This raises the threshold at which columns are declared linearly dependent (from typically 1e-12).
- 2. Set 'maxiter=100' in the Proc Mixed statement This increases the number of convergence iterations used from a default of 50.
- 3. Set 'scoring=4' to specify use of the Fisher scoring algorithm in the first 4 iterations.
- 4. Include the statement 'performance nothread' this removes multi-threading from the calculations.

- 5. Provide starting values for covariance parameters using a 'parms' statement.
- 6. Use a simpler covariance matrix: Should none of the previous methods work, the covariance matrix will be changed from unstructured to Toeplitz with heterogeneous variances (TOEPH). Should this also not converge, a standard Toeplitz matrix (TOEP) will be fitted. Finally, if convergence still does not occur, then an order-1 autoregressive matrix (AR(1)) will be fitted.
 - In this case, the final choice of covariance matrix will be documented in the CTR.

7.5.2 (Other) Secondary endpoint(s)

Secondary endpoints will be analyzed as described in section 7.3.2 in the revised CTP:

Time to change in antipsychotic medication will be analysed in the same manner as the primary endpoint using the stratified Cox proportional hazards model.

Additionally, the analyses for suicidal ideation and behaviour as assessed by C-SSRS will be analysed by calculating a relative risk reduction and providing a 95% confidence interval around the RRR.

The following SAS code will be used for RRR:

```
proc freq data=patdata;
  tables trtp*avalc /chisq RELRISK;
  ods output
RelativeRisks=rr(where=(lowcase(STUDYTYPE)='Cohort (Coll Risk)')
rename=(value=compestimate lowercl=complower uppercl=compupper))
ChiSq=chi(where=(lowcase(STATISTIC)='chi-square') rename=prob=comppvalue);
run;
```

The PGI-I score, change in CGI-S and PSP will be summarized descriptively.

For the secondary endpoints summary, the worse case scenario data will be analyzed if multiple assessments are completed during the same visit window.

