**FLOW CHART (Cont.)**

Trial Periods	Screening Period 	Randomized Treatment Period																Withdrawal/ Taper 			Completed Patients		Early D/C Patients			All Patients
																		Follow-up		Early D/C Option 1	Early D/C Options 2-4	F/U 	End of Study			
		2	3	4	5	6	7	8	9	10	11	12	13	14	15	16	17	18	19					EOT 	F/U 	
Visit	1	2	3	4	5	6	7	8	9	10	11	12	13	14	15	16	17	18	19	EOT 	F/U 	EOT 	EOT 	F/U 	End of Study	
Study week	-4		2	4	6	8	10	12	14	16	18	20	22	24	26	28					29	32				
Study day	-28	1	15	29	43	57	71	85	99	113	127	141	155	169	183	197	V16+2	V16+4	V16+7		V16+28				EOT +28 days	
Visit window in days	-28 to -7	N/A	+/-3	+/-3	+/-3	+/-3	+/-3	+/-3	+/-3	+/-3	+/-3	+/-3	+/-3	+/-3	+/-3	+/-3	+/-1	+/-1	+/-1		+/-3			+/-3		
Clinical Global Impressions -Severity (CGI-S)	X	X		X		X		X		X		X		X		X							X			
Clinical Global Impressions-Improvement (CGI-I)												X				X							X			
Patient Global Impressions –Improvement (PGI-I)												X				X							X			
Personal and Social Performance scale (PSP)		X														X							X			
Positive and Negative Syndrome Scale (PANSS)	X	X		X		X		X		X		X		X		X				X	X	X	X			
Columbia Suicide Severity Rating Scale (C-SSRS)	X	X	X	X	X	X	X	X	X	X	X	X	X	X	X	X	X	X	X		X	X	X	X		
Interactive Response Technology (IRT) Use 	X	X		X		X		X		X		X		X		X				X		X	X			
Dispense study drug		X		X		X		X		X		X		X		X 										
Smartphone app training, set-up/ In-clinic drug administration		X																								
Adverse events	X	X	X	X	X	X	X	X	X	X	X	X	X	X	X	X	X	X	X		X	X	X	X		
Concomitant therapy	X	X	X	X	X	X	X	X	X	X	X	X	X	X	X	X	X	X	X		X	X	X	X		
Compliance check			X	X	X	X	X	X	X	X	X	X	X	X	X	X	X	X	X			X	X			
Termination of trial medication																				X		X	X			
Trial Completion																								X		
Vital Status 																								X		

1. Screening Visit procedures are not required to be completed on the same day.
2. Patients will be randomised to either abrupt withdrawal or slow taper of study drug for 7 days. Vital signs, suicidality and adverse events will be closely monitored during this period.

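### Key secondary MMRM: if the fallback reaches TOEP or AR(1), the week-28 standard error is wrong whenever PANSS variance changes over visits; put heterogeneous-variance structures first (cheap improvement)

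*SAP*

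**What the plan says.** SAP 7.5.1, repeating Protocol 7.3.2, specifies the key secondary model: "Visit will be treated as the repeated measure with an unstructured covariance structure used to model the within-patient measurements". Each visit therefore has its own variance. The test concerns one visit: "The treatment comparison will be the contrast between treatments at the endpoint visit". Inference is model-based: "The Kenward-Roger approximation will be used to estimate denominator degrees of freedom and adjust standard errors". The level is two-sided 0.05 or whatever alpha remains after the primary tests.

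Protocol 7.3.2 leaves non-convergence to the SAP. SAP 7.5.1 lists six steps. Steps 1 to 5 are numerical: singularity threshold, iterations, Fisher scoring, threading and starting values. Step 6 simplifies the covariance, first to TOEPH, which keeps a variance per visit, and then: "Should this also not converge, a standard Toeplitz matrix (TOEP) will be fitted". If that fails too, "then an order-1 autoregressive matrix (AR(1)) will be fitted". The final choice is to be documented in the CTR. The text names no sandwich standard error, no other heterogeneous structure after TOEPH, and no sensitivity analysis on the structure used.

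The PANSS row of the Protocol flow chart gives seven post-baseline clinic visits in the treatment period: Visits 4, 6, 8, 10, 12, 14 and 16, at weeks 4 to 28.

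**The concern.** Standard TOEP and AR(1) each have a single variance parameter. Fitted to seven visits, that parameter settles near the average variance over the visits. The week-28 contrast then borrows this average for its standard error in place of the week-28 variance. If the spread of change from baseline is larger at week 28 than earlier, the standard error is too small and the test rejects too often. If it is smaller, the test is conservative. Kenward-Roger allows for estimating the covariance parameters within the chosen structure; it does not correct a wrong structure.

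Growing spread is plausible here. Patients enter in the stable phase under caps on CGI-S, PANSS total and four PANSS items (Protocol 3.3.2). Some will relapse, and relapsed patients may stay in the trial (Protocol 6.2.2). At stake is the validity of a test in the alpha-controlled hierarchy (Protocol 7.2), in the situation the fallback is written for.

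**Working it through.** The plan gives no SD, effect size or power for the PANSS test, so there is no figure of its own to reproduce. Any variance trend below is an assumption.

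**1. Covariance parameters with T = 7 visits.**
- Unstructured: 7 × 8 / 2 = 28
- TOEPH: 7 variances + 6 correlations = 13
- ARH(1) and CSH: 7 + 1 = 8 each
- TOEP: 1 + 6 = 7
- AR(1): 1 + 1 = 2

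**2. Formula.** With complete data and treatment and baseline effects at every visit, the week-28 estimate is the ordinary per-visit one (ignoring the country main effect). So:
- SE ratio r = √(fitted common variance / week-28 variance)
- actual two-sided type I error = 2(1 − Φ(1.96 r))

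**3. Variance rising linearly from 1 (week 4) to R (week 28).** The average variance is (1 + R)/2, so r = √((1 + R)/(2R)).

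| R | r | SE too small by | Type I error |
|---|---|---|---|
| 1.5 | √(2.5/3) = 0.913 | 9% | 7.4% |
| 2 | √(3/4) = 0.866 | 13% | 9.0% |
| 3 | √(4/6) = 0.816 | 18% | 11.0% |

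Large-sample likelihood fits of both TOEP and AR(1), under compound-symmetric (0.6) and autoregressive (0.8) correlation, give the same figures.

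**4. What relapse alone would produce.** Assume constant background variance 1, a share p in relapse rising linearly to its week-28 value, a shift of d SD in relapse, and no recovery. The variance at each visit is 1 + p(1 − p)d². For 20% and d = 2:
- week 28: 1 + 0.16 × 4 = 1.64
- week 4 (p = 0.2/7 = 0.0286): 1.111, so the variance ratio is 1.48
- seven-visit average: 1.392, so r = √(1.392/1.64) = 0.921

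| Share at week 28 | Shift | Variance ratio | Type I error |
|---|---|---|---|
| 10% | 1 SD | 1.07 | 5.4% |
| 10% | 2 SD | 1.29 | 6.4% |
| 20% | 1 SD | 1.13 | 5.7% |
| 20% | 2 SD | 1.48 | 7.1% |

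The 20% end matches the planning figures in Protocol 7.7. With 30% placebo relapse and a hazard ratio of 0.50, the active rate is 1 − 0.70^0.5 = 16.3%, and overall it is (30 + 2 × 16.3)/3 = 20.9%.

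**5. Dropout and finite samples.** Here the SD, not the variance, rises linearly, with 0% or 20% dropout.
- Week-28/week-4 SD ratio 1.25 (variance ratio 1.56): type I error 7.6–7.9%
- SD ratio 1.5 (variance ratio 2.25): 9.8–10.4%
- SD falling to 0.67: 1.2–1.4%, conservative
- Simulated REML AR(1), 129 vs 258 patients, 20% dropout, 800 runs: 3.5% at constant SD and 9.6% at SD ratio 1.5 (Monte Carlo error about 1 percentage point)

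The large-sample SE ratio does not depend on N, so the early recruitment stop (SAP 4) does not remove the effect.

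**6. With the fix.** Under SD ratios of 1.25 to 2.0, ARH(1) and CSH give SE ratios of 1.00–1.05 and type I error of 3.9–5.0%.

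**The case against.** The strongest objection is remoteness. Five numerical remedies and TOEPH must all fail before a homogeneous structure is fitted. The order is pre-specified, tries a heterogeneous structure first, and ends in a reported choice. The documents give no basis for putting a probability on reaching TOEP. This stands, and it keeps the point small.

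The second objection is that the premise is assumed. A reader might infer from stable entry and the 30% placebo relapse rate that variance must grow, and that the test would run at 9–11%. The documents do not support that. They report no PANSS SDs or trend. The entry caps apply to PANSS total and four items at Visit 1, whereas the endpoint is change in the positive subscale from Visit 2. Five of the six relapse criteria need no PANSS rise (Protocol 2.1.2), and relapsed patients may receive additional treatment, so scores can come back down. The 30% is a placebo planning figure only. Relapse alone, as worked above, reaches a variance ratio of about 1.5; ratios of 2–3 need another source of growth.

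Third, the test is confirmatory only after the primary hierarchy passes, and recruitment stopped early with reduced power. A reader might take the figures as the trial's error rate. They are not: they are conditional on both covariance failures and on rising variance.

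Fourth, ARH(1) and CSH are not simpler than what they would precede: 8 parameters against 7 for TOEP and 2 for AR(1). Banning homogeneous structures outright would leave no pre-specified last resort. This stands and shapes the fix.

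Finally, the SAS code announced for this model is not present in the SAP text available, so an option set there cannot be checked.

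**Conclusion.** The point holds as a conditional one. If the fallback reaches TOEP or AR(1), the model-based week-28 SE is too small when the variance of change grows and too large when it shrinks, and nothing in the SAP text corrects for this. On the relapse mechanism the documents suggest, two-sided type I error would be about 5.4–7.1%. It is 7.4% at a variance ratio of 1.5 and 9–11% only at ratios of 2–3, for which the documents give no support. All these sizes rest on assumed variance trends. The contingency is unlikely and affects one secondary test that may never be confirmatory. The planned unstructured analysis is unaffected. Label: cheap improvement.

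**What to change.** In SAP 7.5.1 step 6, after TOEPH, insert ARH(1) and then CSH before any homogeneous structure. Keep TOEP and then AR(1) only as a last resort, so that the key secondary always has a pre-specified analysis. State that with either of them the week-28 contrast will use an empirical (sandwich) standard error and a named degrees-of-freedom method in place of Kenward-Roger. Settle this before unblinding, since a structure chosen afterwards could look data-driven.

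Cost: one or two lines of SAP text and slightly more fallback programming, with no new data. CSH can be mildly conservative when correlations decay with time (3.9% in the check above).

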Statistical methods:	For the primary endpoint of time to relapse, the equality of the hazard rates will be tested by the Wald test for the treatment effect in a stratified Cox proportional hazards model. The model includes treatment as the only covariate and is stratified by country.

	Secondary endpoints will be analysed descriptively using relative risk ratios and 95% confidence intervals.
--	---

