5.2.2 Secondary endpoints

The secondary endpoints are described in **Section 2.1.3 in the revised CTP**:

- Time to new prescription or increase in dose of an ongoing antipsychotic medication.
- Change from baseline in Clinical Global Impressions –Severity (CGI-S) scale score after 28 weeks of treatment.
- Patient Global Impressions-Improvement (PGI-I) scale score after 28 weeks of treatment.
- Suicidal ideation and behaviour as assessed by C-SSRS after 28 weeks of treatment.
- Change from baseline in Personal and Social Performance scale (PSP) score after 28 weeks of treatment.

See section 6.7 for details regarding the definition of "baseline".

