6.6 HANDLING OF MISSING DATA AND OUTLIERS

Assessment of relapse data (primary endpoint):

All patients will be followed up for relapse [...]. Any patient who has not relapsed will be censored in the analysis of the primary endpoint at the time of their planned complete 28-week treatment period. This does not include the T/W period. For AEs that meet the primary endpoint criteria, missing or incomplete AE dates are imputed according to BI standards.

The sensitivity analysis will use the Full Follow-up period to demonstrate the robustness of the results of the main analysis. See revised CTP Section 7.3

PANSS positive symptoms (key secondary analysis)

Change from baseline in PANSS positive symptoms will be evaluated using Mixed effect Model for Repeated Measures (MMRM) approach. This approach allows for missing data, assuming they are missing at random. All patients can be included in the model and missed visits will not be imputed. If a PANSS item is missing, the missing score on that individual PANSS item will not be imputed; if individual PANSS item is missing within a PANSS subscale, this subscale cannot be included in the calculation of the overall PANSS total score. Therefore, patients with missing individual PANSS items will also have a missing PANSS total score at that visit. However, subscale scores will be used for analysis if none of the individual items are missing.

Relative Risk Reduction (RRR)

Per revised CTP Section 7.5.:

All patients in the FAS will be included [...] *regardless of drop-out.*

For

AE dates

Missing or incomplete AE dates are imputed according to BI standards (see "Handling of missing and incomplete AE dates") (3).

PK data

Missing data and outliers of PK data are handled according to Reference (2) and as described in Section 10 of the revised CTP.

In December 2019, during the conduct of the trial, a Visit 8 eCRF page was added to capture
the date and time of the last dose of BI drug intake before the PK sampling performed at Visit
8. For patients who had completed the trial at that time, or patients for whom the visit 8 date
had passed, the data will be used to inform the date and time of the last BI drug
intake.
Sensitivity analysis: the date and time of the last dose of BI drug intake at Visit 8 collected in
the eCRF will be compared to the information recorded in This will be done for

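### Change in CGI-S and change in PSP, two of the five non-key secondary endpoints, have no planned adjusted difference from placebo, which gives up precision and leaves possible dropout bias unaddressed

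*SAP*

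**What the plan says.** SAP 5.2.2 lists five secondary endpoints below the key secondary one. Two of them are "Change from baseline in Clinical Global Impressions –Severity (CGI-S) scale score after 28 weeks of treatment" and "Change from baseline in Personal and Social Performance scale (PSP) score after 28 weeks of treatment". For their analysis, SAP 7.5.2 repeats protocol 7.3.2: "The PGI-I score, change in CGI-S and PSP will be summarized descriptively". SAP 7 sets the usual table content as N, mean, SD, minimum, median and maximum.

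Two general statements mention intervals, but neither reaches these scales. The protocol synopsis says "Secondary endpoints will be analysed descriptively using relative risk ratios and 95% confidence intervals", and SAP 4 promises hazard ratios with 95% intervals. Relative risks and hazard ratios do not apply to a mean change.

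The key secondary endpoint, PANSS positive symptoms, is treated differently. SAP 7.5.1 gives it an MMRM: "The analysis will include the fixed, categorical effects of treatment at each visit, and the fixed continuous effects of baseline at each visit", with a country effect and an unstructured covariance. SAP 6.6 adds a missing-at-random assumption and states "All patients can be included in the model and missed visits will not be imputed". No such rule is visible there for CGI-S or PSP, although part of that section is blacked out. The only extra rule in SAP 7.5.2 is to take the worst rating when several fall in one visit window.

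On data collection, the protocol flow chart schedules CGI-S at the same clinic visits as PANSS: a Visit 2 baseline, then Visits 4, 6, 8, 10, 12, 14 and 16. PSP is scheduled at Visits 2 and 16. Both also have an early-discontinuation entry. Under protocol 6.2.2, a relapsed patient may stay in the trial. After stopping drug (protocol 3.3.4.1), Option 1 keeps regular visits and Option 2 keeps CGI-S by phone but not PSP. Options 3 and 4 collect neither scale after the end-of-treatment and follow-up visits.

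**The concern.** The trial's stated objective is efficacy compared with placebo, yet two named efficacy endpoints end without a planned estimate of that comparison. A reader who wants one must subtract raw means. That subtraction ignores a baseline that was collected and the country stratum used in randomisation, so it is less precise than it need be. It also rests on whoever has a week-28 value. If patients who worsen are less often rated at week 28, and relapse is commoner in one arm, the raw difference can be off.

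Precision matters more here because SAP 4 reports that recruitment stopped early, that power is reduced, and that the results feed preparation of phase III. The model that would help CGI-S is already written for PANSS and uses the same visits.

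**Working it through.** **Step 1. The plan's own figures.** The documents give no SD, effect size or missingness figure for CGI-S or PSP. Step 3 borrows the sample-size assumptions in protocol 7.7 (30% placebo relapse, hazard ratio 0.5, 20% dropout, 2:1 pooled active to placebo, two-sided 0.05, 80% power), so these are checked first.

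- Events = (1.960 + 0.842)² / [(1/3)(2/3)(ln 0.5)²] = 73.51, so 74, as stated.
- With exponential relapse and competing exponential 20% dropout, the mean event probability is (0.271 + 2 × 0.147)/3 = 0.188. Then 73.51/0.188 gives 391 (from unrounded values), against 385 stated, a gap of 1.6%.

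The inputs are understood. They say nothing yet about CGI-S or PSP.

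**Step 2. Precision.** Assume equal variance σ² at baseline and week 28, with correlation ρ.

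- Variance of raw change: 2σ²(1 − ρ).
- Variance after baseline adjustment: σ²(1 − ρ²).
- Ratio: (1 + ρ)/2.

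The documents give no ρ. For assumed values of 0.3, 0.5 and 0.7 the ratio is 0.65, 0.75 and 0.85, a variance saving of 35%, 25% and 15%. It does not depend on the sample size.

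**Step 3. Possible bias in means of available values.** Active relapse at hazard ratio 0.5 is 1 − 0.7^0.5 = 16.3%. Suppose relapse shifts the week-28 score by a fixed amount D, and a share f of relapsers, equal in both arms, has no week-28 rating. Among rated patients the relapser share is r(1 − f)/(1 − rf). The true difference is 0.300 − 0.163 = 0.137 × D.

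| f (assumed) | Placebo | Active | Difference ÷ D | Attenuation |
|---|---|---|---|---|
| 0 | 0.300 | 0.163 | 0.137 | 0% |
| 0.25 | 0.243 | 0.128 | 0.116 | 15.5% |
| 0.50 | 0.176 | 0.089 | 0.088 | 35.9% |
| 0.75 | 0.097 | 0.047 | 0.050 | 63.2% |
| 1 | 0 | 0 | 0 | 100% |

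(Attenuation is from unrounded values.) The direction also depends on f being equal across arms. With f = 0 on placebo and 0.5 on active, the difference would be 0.300 − 0.089 = 0.211, larger than the true 0.137.

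**Step 4. What a likelihood analysis recovers for CGI-S.** This is a simulation whose inputs are all assumptions except the relapse rates: 60,000 patients per arm, seven post-baseline visits, SD 0.7, within-patient correlation 0.6, relapse adding 1.5 points, the first relapsed rating recorded before dropout, and about 10% unrelated dropout. A multivariate-normal likelihood fit by arm stands in for the MMRM.

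| f | Missing at week 28, active / placebo | True | Available values | Likelihood | Attenuation: available / likelihood |
|---|---|---|---|---|---|
| 0 | 10.0% / 9.9% | −0.201 | −0.202 | −0.202 | about 0 / 0 |
| 0.25 | 13.3% / 16.1% | −0.197 | −0.168 | −0.184 | 14.3% / 6.4% |
| 0.50 | 16.3% / 21.8% | −0.201 | −0.138 | −0.172 | 31.3% / 14.5% |
| 0.75 | 19.6% / 28.0% | −0.202 | −0.092 | −0.145 | 54.6% / 28.1% |

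The likelihood analysis roughly halves the bias. It does not remove it.

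**Step 5. PSP.** With one scheduled post-baseline visit, ANCOVA at Visit 16 uses the same patients as the raw summary. The gain in Step 2 applies; the dropout question in Step 3 is left as it was.

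**The case against.** The strongest reply is that nothing here is wrong. Protocol and SAP agree, formal inference is reserved for relapse and PANSS positive, and describing lower-ranked endpoints is a common choice in phase II. That stands: this is an improvement to offer. It is also true that the tables, with N, mean and SD, let a reader work out an unadjusted difference and interval, so it would go too far to say the endpoints cannot inform the comparison. The synopsis sentence is not a broken promise either, since it calls the secondary analyses descriptive.

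A reader might go further and infer that the planned summaries are observed-case and are biased by relapse-related dropout, and that the MMRM would cure this. The documents do not support that reading. Neither uses the term observed-case; it would be inferred from silence in a partly blacked-out section. Neither says that patients who worsen leave more often. Relapse does not force exit, and Options 1 and 2 keep CGI-S ratings. The dropout figure is 20% overall, with no split by arm. And an MMRM recovers the truth only if the data are missing at random.

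PGI-I sits in the same sentence and might seem to be left out. It rates improvement since randomisation and has no baseline value, so the precision argument does not carry over to it.

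**Conclusion.** The point holds as a worthwhile, inexpensive addition. Two named efficacy endpoints have no planned adjusted difference from placebo, no interval and no visible missing-data rule. The precision loss is the firm part: 15% to 35% of the variance of a raw change comparison over assumed ρ of 0.7 to 0.3, given equal variances at the two times.

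The bias is possible and of unknown size. On the trial's own relapse assumptions, with an equal unrated share in both arms, attenuation of the relapse-driven difference runs from 0% to 100%, and is 15.5% to 35.9% if a quarter to a half of relapsers are unrated. The documents do not say where in that range the trial lies. PSP is more exposed than CGI-S, because the Option 2 phone assessments omit it.

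**What to change.** In SAP 7.5.2, keep the descriptive tables and add:

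- **Change in CGI-S:** the SAP 7.5.1 MMRM with treatment-by-visit, baseline-by-visit and country terms, the same covariance and convergence steps, and the contrast at week 28. State that it handles dropout under missing at random and reduces, but may not remove, bias from relapse-related dropout.
- **Change in PSP at Visit 16:** ANCOVA on baseline and country. State that this gains precision and does not remedy dropout.
- **Reporting:** pooled and per-dose differences from placebo with 95% intervals, labelled nominal and outside the alpha hierarchy.

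In SAP 6.6, state the missing-data rule for both scales. A count by arm of relapsers with and without a week-28 rating would show the share on which Step 3 depends.

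The cost is two more model runs on data already collected. The drawbacks are a few more nominal intervals, and a 7-point ordinal scale (CGI-S) treated as continuous.
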